7 STUDY SCHEDULE

No study procedures should be performed prior to the signing of the informed consent form (ICF). All subjects will sign an ICF prior to undergoing any study tests or procedures. Visit windows (± 3 days) are consecutive calendar days and the target visit dates are calculated from the Baseline Visit.

7.1 Screening Visit

The following procedures will be performed at an office visit to determine the subject's eligibility for the study:

- Obtain written informed consent from subject
- Assess inclusion and exclusion criteria
- Obtain medical history and demographics
- Obtain ALS diagnosis history
- Perform physical examination
- Perform neurological examination (including UMN-B for the Imaging group)
- Measure vital signs including height and weight
- Collect blood and urine for safety labs
- Collect blood for TSPO testing (Imaging group ONLY)
- Perform ECG
- Review and document concomitant medications and therapies
- Assess and document AEs

If time permits, ATLIS (strength testing) will be performed for all participants at the screening visit. This may facilitate a more accurate baseline assessment as some individuals may benefit from a learning effect.

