SI	Site Investigator
SMC	Safety Monitoring Committee
SOP	Standard Operating Procedure
SVC	Slow Vital Capacity
Tregs	T regulatory cells
US	United States
VC	Vital Capacity
WOCBP	Women of Childbearing Potential

PROTOCOL SUMMARY

Study Title

A PILOT STUDY OF RNS60 IN ALS

Version Number

6.0

Protocol Number

RNS60-01

Study Indication

Amyotrophic Lateral Sclerosis (ALS)

[figure not shown]
Phase of Development

IIa

Rationale for the Study

Amyotrophic lateral sclerosis (ALS) is a fatal, neurodegenerative disease for which there is no cure.

A substantial body of evidence implicates the neuroimmune system and specifically activated microglia in ALS pathophysiology. Activated microglia are increased in postmortem brain and spinal cord tissue from patients with ALS compared to healthy controls, and the number of activated microglia correlates positively with faster rate of disease progression. In addition, studies of blood cells in people with ALS have shown an increased activation of two of the major inflammatory cell types in the body, monocytes and T cells. Among T cells, regulatory T cells (Tregs) have been recently proposed to play a role in ALS progression. Tregs and their FoxP3 protein expressions were reduced in rapidly progressing ALS patients and inversely correlated with progression rates. A 3.5-year prospective study revealed that early reduced FoxP3 levels were predictive of future rapid progression and attenuated survival. These data suggest that Tregs may influence disease progression rates in ALS.

[REDACTED]

[REDACTED]

[REDACTED]

Study Design

This is a single center, open label, pilot trial of RNS60 in people with ALS. Study participants will receive study drug for 24 weeks following the core study schedule of activities. Upon nearing completion of the core study, subjects will be given the option to continue to receive drug for approximately an additional 24 weeks, for a total of approximately 48 weeks on study drug, following the optional extension phase schedule of activities.

Study Objectives and Endpoints

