RNS60 infusion		X	X	X	X	X			
RNS60 Dispensing (for inhalation)		X	X (week 7)		X (week 15)				
RNS60 Accountability			X	X	X	X			X
AE review ⁸	X	X	X	X	X	X	X		X
Concomitant Meds	X	X	X	X	X	X	X		X
Collection of blood biomarkers		X		X		X			X

¹ Screening procedures must be completed within 6 weeks prior to Baseline Visit.

RNS60 in ALS

V6.0

5/5/2016

² Follow-up will continue every 3 months up to 2 years to collect data on SVC, ALSFRS-R, and survival status. This information may be obtained via chart review and patient contact.

³ Follow-up phone call to occur 28 +5 days after the last dose of study drug if a subject discontinues from the study prematurely.

⁴ Safety labs include Hematology (CBC with differential), Complete Chemistry Panel, Liver Function Tests, Urinalysis, Urine pregnancy test (WOCBP).

⁵ Vital signs include systolic and diastolic pressure in mmHg, respiratory rate/minute, heart rate/minute, temperature and weight. Height measured at Screening Visit only.

⁶ The Penn Upper Motor Neuron-Burden (UMN-B) includes testing of reflexes, the CNS Lability Scale (CNS-LS) and the Ashworth Spasticity Scale.

⁷ If time permits, ATLIS will be performed at the screening visit.

⁸ Adverse events that occur AFTER signing the informed consent form will be recorded.

^{*Off}treatment [¹¹C]PBR28-PET will be performed one time only between the Screening and Baseline visit. ALSFRS-R and SVC will be repeated on the day of the scan.

^{**On}treatment [¹¹C]PBR28-PET will be performed one time only between the Week 18 and Week 23 visits. ALSFRS-R and SVC will be assessed the day of the scan ONLY.

[†]For subjects in the “Imaging group” only.

SCHEDULE OF ACTIVITES – OPTIONAL EXTENSION PHASE

	Weekly visits Week 24 through Week 34	Week 35	Weekly visits Week 36 through Week 46	Week 47	Week 52 Phone Call	Follow Up Chart Review / Phone Call ²	Final Safety Visit (for early study drug discontinuation only) ¹
Visit Window	Day 168 ± 3	Day 245 ± 3	Day 252 ± 3	Day 329 ± 3	Day 364 ± 3	Every 3 months	
12-lead ECG		X		X			X
Safety Labs ³		X		X			X
Vital Signs / Weight ⁴	X	X	X	X			X
Neurological exam				X			X
Physical exam				X			X
ALSFRS-R		X		X	X	X	X
Slow Vital Capacity		X		X		X	X
C-SSRS		X		X			X
RNS60 infusion	X	X	X	X			
RNS60 Dispensing (for inhalation)	X (week 30)		X (week 38)				
RNS60 Accountability	X	X	X	X			X
AE review ³	X	X	X	X	X		X
Concomitant Meds	X	X	X	X	X		X

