3.2 Study Outcome Measures

For all subjects enrolled in the study, the following will be primary outcome measures:

- 1- Safety, as measured by AEs and clinically meaningful changes in vital signs, physical examination, and standard clinical laboratory tests;
- 2- Tolerability, defined as the ability of subjects to complete the entire 24-week treatment portion of study;
- 3- Clinical outcomes: Measured by ALSFRS-R, SVC, and strength (measured by ATLIS).
- 4- Blood biomarkers of inflammation.

For subjects in the “Imaging group”, the following additional outcome measures will be obtained:

- 1- Neuroimaging biomarkers ([¹¹C]-PBR28-PET) including both regions of interest (ROI) and voxel-based analyses

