7.2 Baseline Visit

This visit will take place within 6 weeks of the Screening Visit. The following procedures will be performed:

- Review inclusion and exclusion criteria
- Measure vital signs including weight
- Collect blood and urine for safety labs
- Perform ECG
- Collect blood samples for biomarkers
- Administer ALSFRS-R questionnaire
- Perform U. Penn upper motor Neuron Burden (UMNB)
- Perform Pulmonary Function Tests
- Measure baseline strength (ATLIS)
- Columbia Suicide Severity Rating Scale (C-SSRS) – Baseline
- Administer 1st dose of study drug.
- Dispense study medication (for inhalation use) for the following 8 weeks
- Review and document concomitant medications and therapies
- Assess and document AEs

Pre- treatment neuroimaging study (MRI/PET) (Imaging group only) will take place after TSPO affinity test results are available. This may occur on any day between release of TSPO test results and Baseline, or on the same day as the Baseline Visit. This first neuroimaging study will be performed before any treatment is administered. ALSFRS-R and SVC will be repeated on the same day as the scan. STAT quantitative serum human chorionic gonadotropin (hCG) testing will also be performed prior to the MRI/PET scan for all women of childbearing potential (WOCBP).

7.3 Weekly study visits (Week 1 through Week 10, Week 12 through Week 22, Week 24 through 34, and Week 36 through 46)

Subjects will return to MGH on a weekly basis until Week 22. The following procedures will be performed at the Week 1 through Week 10, Week 12 through Week 22, Week 24 through 34, and Week 36 through 46 visits:

- Vital signs including weight
- Administer study drug via IV infusion
- Review and document concomitant medications and therapies
- Assess and document AEs
- Check study drug compliance and accountability
- Dispense study medication (for inhalation use) (at Week 7, Week 15, Week 23, Week 30 and Week 38 only)

Post-treatment neuroimaging study (MRI/PET) (Imaging group only) will be performed at one time only between the Week 18 and Week 23 visits. ALSFRS-R and SVC will be repeated on the

same day as the scan. STAT quantitative serum hCG testing will also be performed prior to the MRI/PET scan for all WOCBP.

Subjects who wish to continue to take study drug as part of the optional extension phase will sign consent between Weeks 18 and 23.

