8.1.11 Strength measurement (ATLIS)

Changes in strength will be measured using ATLIS (Accurate Test of Limb Isometric Strength), a non-invasive device that allows measurements of isometric strength in 12 muscle groups of the arms and legs using a standard protocol (elbow and knee flexion and extension, grip, and dorsiflexion). ATLIS consists of a frame with metal uprights. A wireless load cell is attached to adjustable testing stations positioned on the frame. The load cell transmits data (peak force) to a laptop computer using wireless technology. The General Hospital Corporation was granted a patent for this device by the US Patent Office (Patent # 7,493,812 issued 2/24/09). This device is not FDA approved.

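### The ATLIS practice session depends on available time, so any learning gain in subjects first tested at Baseline would count as change in strength, with no control arm to cancel it

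*Combined protocol and SAP*

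**What the plan says.** The screening ATLIS session is conditional in both places that describe it. Section 7.1 says "If time permits, ATLIS (strength testing) will be performed for all participants at the screening visit", and footnote 7 to the core Schedule of Activities says "If time permits, ATLIS will be performed at the screening visit". The schedule itself marks ATLIS at Screening, Baseline, Week 11, Week 23 and the Final Safety Visit. The extension schedule has no ATLIS.

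Section 7.1 gives the purpose of the early session: "This may facilitate a more accurate baseline assessment as some individuals may benefit from a learning effect".

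The Baseline Visit list in section 7.2 includes "Measure baseline strength (ATLIS"), and section 8.1.11 frames the outcome as change: "Changes in strength will be measured using ATLIS (Accurate Test of Limb Isometric Strength"). Section 3.2 includes, among the primary outcome measures for all subjects, "Clinical outcomes: Measured by ALSFRS-R, SVC, and strength (measured by ATLIS"). The Protocol Summary describes the design: "This is a single center, open label, pilot trial of RNS60 in people with ALS".

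Section 6.7 gives no analysis of ATLIS. It has no model, standard deviation, significance level, adjustment for prior practice or sensitivity analysis for strength.

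**The concern.** The protocol names a possible weakness in its own baseline measurement and provides a safeguard, then lets the safeguard lapse when a visit runs long. The baseline may then mix people who have done the test before with people who have not.

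In a randomised trial a practice gain would fall on both arms and largely cancel in the comparison. Here every treated subject receives RNS60, so a gain between the first and second test goes straight into the change from Baseline. Strength in ALS normally falls, so the likely appearance is a slower decline rather than a net rise. Either way the error favours the drug. It also cannot be repaired later: once a subject has been dosed, a practised pre-treatment baseline can no longer be obtained.

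**Working it through.** The plan states no figure for ATLIS, so there is none to reproduce. The check is of direction and of how the bias scales.

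**Inputs from the documents.** ATLIS at Baseline, Week 11 and Week 23 (core schedule); practice session conditional (7.1, footnote 7); single arm (Protocol Summary); 18 treated subjects (3.1), although 5.1 and 6.7 use 15.

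**Inputs not in the documents.**
- f, the share of subjects with no ATLIS session before Baseline.
- L, the mean learning gain over all unpractised subjects, including those who gain nothing. If only a share r of them gain, by an amount g, then L = r x g.

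**Step 1: one subject.** Observed change = true change + (practice effect at the later visit - practice effect at Baseline). If one earlier session is enough to exhaust learning, the bracket is 0 for a practised subject. For an unpractised subject it averages L.

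**Step 2: the group mean.** Bias = f x L + (1 - f) x 0 = f x L. With 18 subjects, each unpractised subject adds L/18.

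**Step 3: illustrative values.** L = 3% to 10% of baseline strength is an assumption, and so is f, which is taken from 0 upward.

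| f | L = 3% | L = 10% |
|---|---|---|
| 0 | 0 | 0 |
| 0.25 | 0.75 | 2.5 |
| 0.5 | 1.5 | 5.0 |
| 0.75 | 2.25 | 7.5 |

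Entries are percentage points of baseline strength. Per unpractised subject among 18, the mean moves by 3/18 = 0.17 to 10/18 = 0.56 points.

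**Step 4: would a slope analysis avoid it?** Take times 0, 11 and 23 weeks.
- Mean time = 34/3 = 11.33.
- Sum of squared deviations = 11.33² + 0.33² + 11.67² = 264.67.
- A Baseline value too low by L, with the gain fully present by Week 11, raises the least-squares slope by 11.33 x L / 264.67 = 0.0428 L per week.
- Over 23 weeks that is 0.0428 x 23 x L, or about 0.98 L.

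A slope therefore carries almost the whole bias. The change from Week 11 to Week 23 would escape it, if learning were complete by Week 11, but no such analysis is specified.

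**Step 5: with the safeguard made standard.** f = 0 gives a bias of 0 x L = 0, provided one session exhausts learning. The documents do not say that it does.

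**The case against.** **The learning effect is only a possibility.** A reader might infer that the plan expects learning and that measured change is therefore biased upward. The text supports less: it says practice may help and that some individuals may benefit. The bias is conditional on a gain occurring. This stands.

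**The size is unknown.** Both f and L are assumed. The schedule marks ATLIS at Screening and the session is meant for all participants when time allows, so f could be near 0. The 7.5-point corner of the table multiplies two unsupported extremes. This stands, and the table shows scaling only.

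**Missed practice might track illness or fatigue.** That is a tempting further step, but the protocol names only time as the reason for omitting the session. The documents do not support it.

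**ATLIS may not really be primary.** Section 3.2 lists it under primary outcome measures. The Protocol Summary, however, sets the clinical outcomes apart from the primary objectives, section 3.1 says only that they will be collected, and section 6.7 bases the sample size on safety and tolerability. No ATLIS test or success threshold exists, so false-positive rates would describe a test that is not planned. This limits the weight of the point but does not remove it, because 3.2 is explicit.

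**An uncontrolled pilot cannot attribute strength change to the drug in any case.** That is true, and the documents give no reference rate of decline. It is still no reason to leave in place an avoidable error that the protocol itself names.

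**Some safeguards already exist.** Section 7.2 labels the Baseline-visit session as baseline strength. Section 11 sends all collected data to the EDC, so a completed screening test would itself show practice status. Both are right. What is missing is the requirement to practise and a prespecified use of practice status.

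**Conclusion.** The point holds in conditional form. The protocol allows for a learning effect on ATLIS and leaves the practice session to available time. In this single-arm design, any gain in subjects first tested at Baseline would add to their measured change at Week 11 and Week 23. The direction follows from the design, given that a gain occurs after Baseline. The size, f x L, cannot be obtained from the documents and may be near zero if almost everyone is tested at screening.

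A reader might go further and conclude that the trial's main results are compromised. They are not: safety, tolerability, blood biomarker and PET outcomes do not depend on ATLIS, and neither does the sample size. This is a low-cost improvement to one listed outcome and worth making before subjects are dosed.

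**What to change.** - In section 7.1 and in footnote 7 of the core schedule, remove the time condition, so that every subject has one ATLIS session at screening or on another day before Baseline.
- Do not place the practice session on the Baseline day. ATLIS tests 12 muscle groups (8.1.11) and that visit is already full. Fatigue from a second session could lower the Baseline score and inflate later change, which is the error to be avoided.
- Keep the Baseline-visit session as the analysis baseline, as 7.2 already labels it, and say so in section 6.7.
- In section 6.7, prespecify a repeat of the strength analysis that excludes any subject who still missed the practice session.

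The cost is added time at the screening visit and some practice tests on people who are never treated: about 25 - 18 = 7, on the numbers in section 4.1. One session may reduce learning without removing it, so the report should still mention residual learning as a limitation.

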7.1.1 Screen Failures

Any subject who signs consent will be considered enrolled in the study. If a subject fails screening, *at a minimum*, the following information should be captured and entered in the Electronic Data Capture (EDC) System:

- Demographics
- Inclusion and Exclusion criteria
- Reason for screen failure
- Screening labs results

7.2 Baseline Visit

This visit will take place within 6 weeks of the Screening Visit. The following procedures will be performed:

- Review inclusion and exclusion criteria
- Measure vital signs including weight
- Collect blood and urine for safety labs
- Perform ECG
- Collect blood samples for biomarkers
- Administer ALSFRS-R questionnaire
- Perform U. Penn upper motor Neuron Burden (UMNB)
- Perform Pulmonary Function Tests
- Measure baseline strength (ATLIS)
- Columbia Suicide Severity Rating Scale (C-SSRS) – Baseline
- Administer 1st dose of study drug.
- Dispense study medication (for inhalation use) for the following 8 weeks
- Review and document concomitant medications and therapies
- Assess and document AEs

Pre- treatment neuroimaging study (MRI/PET) (Imaging group only) will take place after TSPO affinity test results are available. This may occur on any day between release of TSPO test results and Baseline, or on the same day as the Baseline Visit. This first neuroimaging study will be performed before any treatment is administered. ALSFRS-R and SVC will be repeated on the same day as the scan. STAT quantitative serum human chorionic gonadotropin (hCG) testing will also be performed prior to the MRI/PET scan for all women of childbearing potential (WOCBP).

7.3 Weekly study visits (Week 1 through Week 10, Week 12 through Week 22, Week 24 through 34, and Week 36 through 46)

Subjects will return to MGH on a weekly basis until Week 22. The following procedures will be performed at the Week 1 through Week 10, Week 12 through Week 22, Week 24 through 34, and Week 36 through 46 visits:

- Vital signs including weight
- Administer study drug via IV infusion
- Review and document concomitant medications and therapies
- Assess and document AEs
- Check study drug compliance and accountability
- Dispense study medication (for inhalation use) (at Week 7, Week 15, Week 23, Week 30 and Week 38 only)

Post-treatment neuroimaging study (MRI/PET) (Imaging group only) will be performed at one time only between the Week 18 and Week 23 visits. ALSFRS-R and SVC will be repeated on the

same day as the scan. STAT quantitative serum hCG testing will also be performed prior to the MRI/PET scan for all WOCBP.

Subjects who wish to continue to take study drug as part of the optional extension phase will sign consent between Weeks 18 and 23.

7.4 Week 11 Visit

The following procedures will be performed at the Week 11 visit:

- Measure vital signs including weight
- Collect blood and urine for safety labs
- Collect blood for biomarkers
- Administer ALSFRS-R questionnaire
- Perform U. Penn upper motor Neuron Burden (UMNB)
- Perform Pulmonary Function Tests
- Measure strength (ATLIS)
- Columbia Suicide Severity Rating Scale (C-SSRS) – Since last visit
- Administer study drug via IV infusion
- Check study drug compliance and accountability
- Review and document concomitant medications and therapies
- Assess and document AEs

7.5 Week 23 Visit

The following procedures will be performed at the Week 23 visit:

- Measure vital signs including weight
- Perform ECG
- Perform neurological exam
- Perform physical exam
- Collect blood and urine for safety labs
- Collect blood for biomarkers
- Administer ALSFRS-R questionnaire
- Perform U. Penn upper motor Neuron Burden (UMNB)
- Perform Pulmonary Function Tests
- Measure strength (ATLIS)
- Columbia Suicide Severity Rating Scale (C-SSRS) – Since last visit
- Administer study drug via IV infusion
- Review and document concomitant medications and therapies
- Assess and document AEs
- Check study drug compliance
- For those subjects that do not wish to continue, perform study drug accountability and collect all unused study drug, empty containers and nebulizers
- For those subjects that wish to participate in the 24-week extension phase, medication for inhalation will be dispensed at this visit

7.6 Week 35 Visit

The following procedures will be performed at the Week 35 visit:

- Measure vital signs including weight
- Perform ECG
- Collect blood and urine for safety labs
- Administer ALSFRS-R questionnaire
- Perform Pulmonary Function Tests
- Columbia Suicide Severity Rating Scale (C-SSRS) – Since last visit
- Review and document concomitant medications and therapies
- Assess and document AEs
- Check study drug compliance and accountability

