Subjects will remain on treatment in the core study for 24 weeks. Each subject will also have a Week 28 Follow-up Telephone Interview to assess for adverse events (AEs), changes in concomitant medications and to administer the ALSFRS-R. After the completion of the trial, subjects will be called by phone approximately every 3 months to ascertain ALSFRS-R and vital status for up to 2 years.

Optional Extension Phase

Upon nearing completion of the core study, subjects will be given the option to continue RNS60 treatment for an additional 24 weeks of weekly infusions and daily inhalations. Subjects interested in continuing treatment in the extension phase will sign an additional IRB-approved consent addendum document with the physician-investigator during a clinic visit between Week 18 and Week 23. Extension phase drug dispensing will occur at the Week 23 visit. Safety parameters such as blood work, urine samples, EKGs, and adverse event recording will continue to be monitored during the extension phase. ALSFRS-R and SVC outcome measures will be collected at two time points. Each subject will also have a Week 52 Follow-up Telephone Interview to assess for adverse events (AEs), changes in concomitant medications and to administer the ALSFRS-R. After the completion of the trial, subjects will be called by phone approximately every 3 months to ascertain ALSFRS-R and vital status for up to 2 years.

Subjects may choose to discontinue RNS60 treatment at any point during the optional extension phase.

SCHEDULE OF ACTIVITES – CORE STUDY

	Screening Visit ¹	Baseline Visit	Weekly visits Week 1 through Week 10	Wk 11 Visit	Weekly visits Week 12 through Week 22	Week 23 Visit	Week 28 Phone call	Follow Up Chart Review / Phone Call ²	Final Safety Visit (for early study drug discontinuation only) ³
Visit Window	-42 days	Day 0	Day 7 ± 3	Day 77 ± 3	Day 84 ± 3	Day 161 ± 3	Day 196 ± 5	Every 3 months	
Informed Consent	X								
Eligibility Criteria	X	X							
Demographics	X								
ALS History / ALS Diagnosis	X								
Medical History	X								
Blood sample for TSPO Affinity test†	X								
12-lead ECG	X	X				X			X
Safety Labs ⁴	X	X		X		X			X
Vital Signs /Height and weight ⁵	X	X	X	X	X	X			X
Neurological exam	X					X			X
Physical exam	X					X			X
[¹¹ C]PBR28-PET†		X*			X**				
ALSFRS-R		X*		X	X**	X	X	X	X
U Penn Upper Motor Neuron Burden ⁶	X	X		X		X			X
Slow Vital Capacity		X*		X	X**	X		X	X
Strength measurement (ATLIS) ⁷	X	X		X		X			X
C-SSRS		X		X		X			X

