6.4 Accountability Procedures

Subjects will be provided with a drug diary at each time point when drug for inhalation is dispensed (baseline, week 7, and week 15 for the core study, and week 23, week 30, and week 38 for the extension phase). Subjects will be instructed to return all drug for inhalation consumed and remaining, as well as a completed diary, at weeks 7, 15, 23, 30, 37, and 47. Reconciliation of drug consumed and drug remaining will be logged on the drug dispensing and return log, signed and dated. Any discrepancies noted will be investigated, resolved, and documented prior to return or destruction of unused study drug. Drug destroyed on site will be documented in the study files.

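### In the optional extension, the Week 35 and Week 47 visit lists omit an infusion that the schedule marks, and inhalation drug is returned at Week 37 but re-dispensed at Week 38

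*Combined protocol and SAP*

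**What the plan says.** **Infusion.** The protocol summary (Optional Extension Phase) offers "an additional 24 weeks of weekly infusions and daily inhalations". Section 6.1.2 gives intravenous RNS60 at each weekly clinic visit from Baseline onward. In the table headed "SCHEDULE OF ACTIVITES – OPTIONAL EXTENSION PHASE", the infusion row reads "RNS60 infusion X X X X": one mark each for Weeks 24 to 34, Week 35, Weeks 36 to 46 and Week 47.

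Section 7.3 lists the infusion for the ordinary weekly visits, but in the extension it covers only Weeks 24 to 34 and 36 to 46. Weeks 35 and 47 have their own sections. Section 7.6 begins "The following procedures will be performed at the Week 35 visit" and gives nine items. Section 7.7 gives twelve. Neither includes an infusion. The lead-in to 7.7 names the Week 23 visit although the section is titled Week 47.

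**Inhalation supply.** Section 6.4 dispenses inhalation drug for the extension at Weeks 23, 30 and 38. In the same paragraph it asks subjects to bring back all of it, used and unused, with the diary, "at weeks 7, 15, 23, 30, 37, and 47". Section 6.5 repeats those weeks for empty containers. Section 7.3 dispenses "at Week 7, Week 15, Week 23, Week 30 and Week 38 only", and the extension schedule also shows Week 38. Section 7.2 states the Baseline supply as 8 weeks. Section 6.2.3, on dispensing, is redacted.

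**The concern.** Visit lists and accountability rules are what staff work from. The omission in 7.6 and 7.7 is not the protocol's usual style, because the matching core sections, 7.4 (Week 11) and 7.5 (Week 23), both list the infusion. The visible text gives no order of precedence between the schedule and the visit lists.

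The Week 37 return date also breaks a pattern: at every other interim return, the next supply is handed out at the same visit.

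At stake is what dose was due in the extension. Under 6.5, site staff judge compliance from returned medication, and under 6.4 any discrepancy must be investigated and resolved. If the dose due differs from one section to another, the same conduct can be compliant under one and a deviation under another. Extension safety data would then be read against an uncertain intended exposure.

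**Working it through.** No power or sample-size formula applies. The check is a count of visits and a comparison of weeks.

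**1. Infusions in the extension schedule**
- Weeks 24 to 34: 34 − 24 + 1 = 11
- Week 35: 1
- Weeks 36 to 46: 46 − 36 + 1 = 11
- Week 47: 1
- Total: 11 + 1 + 11 + 1 = **24**, which reproduces the summary's 24 weeks of weekly infusions.

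**2. Infusions in the Section 7 lists**
- Section 7.3: 11 + 11 = 22
- Sections 7.6 and 7.7: 0 + 0
- Total: **22**
- Difference: 24 − 22 = 2, and 2/24 = 8.3% of extension infusions.
- Core infusions at Baseline and Weeks 1 to 23 number 1 + 23 = 24. Over both phases the totals are 24 + 24 = 48 by the schedules and 24 + 22 = 46 by the lists.

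**3. Return week against next dispensing week**

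| Return (6.4) | Next dispensing (6.4, 7.3) | Gap in weeks |
|---|---|---|
| 7 | 7 | 0 |
| 15 | 15 | 0 |
| 23 | 23 | 0 |
| 30 | 30 | 0 |
| 37 | 38 | 1 |

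Four of the five pairs coincide. The sixth return, at Week 47, ends treatment and has no dispensing after it.

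**4. Size of the inhalation gap**
- Inhalation is due on 6 days a week (6.1.2). From dispensing at Week 23 to the last return at Week 47 is 47 − 23 = 24 weeks, so 24 × 6 = 144 scheduled inhalation days.
- At nominal spacing, the days between the Week 37 and Week 38 infusion visits are 6 inhalation days.
- If unused drug is handed back to the subject after the Week 37 count, 0 days are affected. If it is kept, up to about 6 are: 6/144 = 4.2%. The range is therefore **0 to about 6 days**.

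**5. What the visible supply quantity adds**
- Only the Baseline quantity, 8 weeks, is visible. If the Week 30 supply were also 8 weeks (an assumption), it would run to 30 + 8 = Week 38. That does not resolve the conflict, because the Week 37 return instruction would still stand.

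**The case against.** The strongest case on the other side is that these are copy-editing slips.

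*Infusion.* No text withholds an infusion at Week 35 or Week 47. The summary, the schedule and 6.1.2 agree with one another, and the wrong week in the 7.7 lead-in suggests copied text. A reader might infer that the protocol directs staff to skip two infusions. It does not: the conflict is by omission, and the 8.3% is a ceiling reached only if staff follow the lists alone. This part of the objection stands. It does not make the lists correct, since they are presented as the procedures for those visits and 7.3 does not cover the two weeks.

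*Inhalation.* A reader might infer that subjects certainly go a week without drug. The documents do not establish that. Section 6.5 asks only for empty containers, which removes no usable drug. An explicit instruction to collect all unused drug appears only where treatment ends: 7.5 for those not continuing, 7.7 and 7.9. The handling of unused drug at an interim return may be described in the redacted 6.2.3. This also stands, so the gap is conditional. The mismatch between Weeks 37 and 38 remains whatever 6.2.3 says, because both weeks appear in the visible text of 6.4.

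*Consequence.* A reader might go further and infer that planned exposure or compliance summaries will be distorted. Section 6.7 specifies no exposure-based safety summary and no compliance denominator, so that effect cannot be claimed.

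**Conclusion.** The point holds as a minor inconsistency in operative instructions, confined to the optional extension. The Section 7 lists give 22 infusions where the schedule gives 24, and one of the five return and re-dispensing pairs is a week apart. The infusion count rests on reading 7.6 and 7.7 as complete lists. The inhalation figure, up to about 6 of 144 days, rests on unused drug being kept at Week 37, which the visible text leaves open. Quantities supplied after Baseline are not visible, and nothing is concluded about whether supply was sufficient.

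Tolerability is defined on the 24-week core treatment period, before either discrepancy arises. The core endpoints, sample size and power are unaffected. The effect is limited to intended extension exposure and to what counts as compliance or a deviation.

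**What to change.** - Reconcile 7.6 and 7.7 with the extension schedule, the summary and 6.1.2 on the infusion at Weeks 35 and 47.
- Correct the visit named in the 7.7 lead-in.
- Reconcile the return week in 6.4 and 6.5 with the dispensing week in 6.4, 7.3 and the schedule. If 6.2.3 does not already do so, state what happens to unused drug at an interim return.
- Judge extension compliance against the reconciled dosing days.

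Which version applies is for the sponsor to decide. The cost is protocol wording only, with no change to sample size, assessments or core analyses.
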